7 DISCONTINUATION OF STUDY INTERVENTION AND PARTICIPANT DISCONTINUATION/WITHDRAWAL

7.1 DISCONTINUATION OF STUDY INTERVENTION

The IMP should be continued whenever possible. In case the IMP is stopped, it should be determined whether the stop can be made temporarily; permanent IMP discontinuation should be a last resort. Any IMP discontinuation should be fully documented in the e-CRF. In any case, the participant should remain in the study as long as possible.

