7.1.1 Permanent discontinuation

In rare instances, it may be necessary for a participant to permanently discontinue study intervention. If study intervention is permanently discontinued, the participant will remain in the study to be evaluated for the assessments planned for the EOT/EOS Visit, with the exception of the CT scan. See the SoA ([Section 1.3](#)) for data to be collected at the time of discontinuation of study intervention and follow-up and for any further evaluations that need to be completed.

Participants must be withdrawn from the study (ie, from any further IMP or study procedure) for the following reasons:

- At their own request or at the request of their LAR (an individual or judicial or other body authorized under applicable law to consent on behalf of a prospective participant to the participant's participation in the procedures involved in the research)
- If, in the Investigator's opinion, continuation in the study would be detrimental to the participant's well-being
- In case of surgery for NP
- At the specific request of the Sponsor
- In the event of a critical protocol deviation, at the request of the Investigator or the Sponsor
- In the event of an anaphylactic systemic allergic reaction that is related to IMP and that requires treatment
- In the event that the participant is diagnosed with a malignancy during the study, excluding carcinoma in situ of the cervix or squamous or basal cell
- Pregnancy
- Any opportunistic infection, such as TB or other infections whose nature or course may suggest an immunocompromised status (refer to Appendix 9 [[Section 10.9](#)])
- Met liver chemistry stopping criteria ([Section 7.1.2](#))

Handling of participants after permanent intervention discontinuation

Participants will be followed up according to the study procedures specified in this protocol up to the scheduled date of study completion or up to recovery or stabilization of any AE to be followed up as specified in this protocol, whichever comes last.

If possible, and after the permanent discontinuation of intervention, the participants will be assessed as soon as possible using the procedures normally planned for the EOT/EOS Visit (refer to SoA [[Section 1.3](#)]).

All cases of permanent intervention discontinuation must be recorded by the Investigator on the appropriate pages of the e-CRF when considered as confirmed.

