7.1.2 Liver chemistry stopping criteria

Details of the liver chemistry stopping criteria are provided in Appendix 5 ([Section 10.5](#)).

Discontinuation of study intervention for abnormal liver tests is required by the Investigator when a participant meets one of the conditions outlined in the algorithm (ie, ALT >3 × ULN) or in the presence of abnormal liver chemistries not meeting protocol-specified stopping rules if the Investigator believes that it is in best interest of the participant.

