8.2.7 Hypersensitivity monitoring

Allergic reaction is a potential risk associated with the administration of most therapeutic monoclonal antibody treatments.

Allergic reactions may be defined as allergic reaction-mediated signs and symptoms experienced by participants during or shortly after a pharmacologic or biologic agent is given. These reactions may present in a variety of ways, including dizziness, headache, anxiety, dyspnea, hypotension, tachycardia, pruritus, rash, urticaria/angioedema, flushing, nausea or vomiting, and joint pain with fever. Allergic reactions may begin within a few hours and persist up to 24 hours after dosing.

Refer to Appendix 12 ([Section 10.12](#)), which describes the clinical criteria for the diagnosis of anaphylaxis.

Participants should be monitored for at least 30 minutes after each study site IMP administration for any signs or symptoms of a hypersensitivity reaction. Any instance of allergic reaction should be reported as an AESI ([Section 8.3.6](#)). Any anaphylactic reactions or acute allergic reactions that require immediate treatment will be an AESI with immediate reporting (within 24 hours), and study medication must be permanently discontinued. Trained personnel and medications should be available to treat anaphylaxis or any severe allergic reaction if it occurs. Furthermore, the study participants will be advised, when the IMP is administered at home, to self-monitor for potential signs and symptoms that may suggest a hypersensitivity reaction for at least 30 minutes after administration.

Anaphylactic reactions or systemic allergic reactions that are related to IMP and require treatment must be reported as an AESI (within 24 hours; for further details, see AESI definition in [Section 8.3.6](#)), and study medication must be permanently discontinued.

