9.3.3 Key secondary efficacy endpoints

- Change from baseline to Week 24 in bilateral NPS
- Change from baseline to Week 24 in NC symptom severity score using the CRSwNP nasal symptom diary (refer to [Section 8.1.2](#) for the details of NC symptom severity score assessment)
- Change from baseline to Week 24 in opacification of sinuses assessed by CT scan using the LMK score (refer to [Section 8.1.3](#) for the details of LMK score)

Handling of missing data

Each of the 3 key secondary efficacy endpoints will be analyzed using a hybrid method of worst-observation carried forward (WOCF) and multiple imputation. For participants taking selected prohibited medications and/or rescue medications or who undergo surgery (details of selection will be specified in the SAP, refer to [Section 6.8.1](#)), their data after the medication usage or surgery will be set to missing, and the worst postbaseline value on or before the time of the medication usage or surgery will be used to impute the missing Week 24 value (for participants whose postbaseline values are all missing, the baseline will be used to impute). Participants who discontinue the treatment prematurely are encouraged to follow the planned clinical visits, and in those participants who did not take the selected prohibited medications and/or rescue medications or undergo surgery, all data collected after treatment discontinuation will be used in the analysis. For these participants, missing data may still happen despite all efforts to collect the data after treatment discontinuation. For participants who discontinue due to lack of efficacy, all data collected after discontinuation will be used in the analysis, and a WOCF approach will be used to impute the missing Week 24 value if needed. For participants who discontinue not due to lack of efficacy, a multiple imputation approach assuming missing at random will be used to impute the missing Week 24 value, and this multiple imputation will use all participants, excluding participants who have taken the selected prohibited medications and/or rescue medications or undergone surgery on or before Week 24 and excluding participants who discontinue due to lack of efficacy on or before Week 24. All of the imputed complete data will be analyzed by descriptive statistics with the 95% CI. The summarized mean changes obtained from each imputed dataset will be combined using Rubin's rule for a single estimate.

Other secondary efficacy endpoints

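### Protocol 7.1.1 withdraws participants with listed safety events from all study procedures, against the follow-up text around it; a few Week 24 scores could be lost (minor wording fix)

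*Protocol*

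**What the plan says.** Protocol 7.1 sets the general rule after a stop of IMP: "In any case, the participant should remain in the study as long as possible". Section 7.1.1 opens in the same sense. A participant who permanently stops IMP stays in the study for the EOT/EOS assessments, "with the exception of the CT scan".

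The next paragraph of 7.1.1 points the other way: "Participants must be withdrawn from the study (ie, from any further IMP or study procedure) for the following reasons". Ten reasons follow.

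- Five are safety events: a related anaphylactic or systemic allergic reaction that needs treatment, malignancy, pregnancy, opportunistic infection, and the liver stopping criteria.
- The other five are the participant's own request, Investigator-judged detriment, surgery for nasal polyps (NP), Sponsor request, and a critical protocol deviation.

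The section then closes under the subheading "Handling of participants after permanent intervention discontinuation" with: "Participants will be followed up according to the study procedures specified in this protocol up to the scheduled date of study completion". No sentence says whether the listed participants are exempt from that follow-up.

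On the analysis side, Protocol 9.3.3 says: "Participants who discontinue the treatment prematurely are encouraged to follow the planned clinical visits". SAP Table 3 labels the use of data collected after treatment discontinuation a treatment-policy strategy for the change-from-baseline endpoints.

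**The concern.** A site with a participant who meets, say, the liver stopping criteria cannot follow both the list and the text on either side of it. If it follows the list early in the study, the Week 24 nasal polyp score (NPS), the diary data and the CT are not collected. The analysis then has to do without off-treatment data that the plan intends to use. The study is small (about 25 participants) and is judged on a point estimate, so each avoidable loss is visible.

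**Working it through.** **1. How the same safety events are treated elsewhere in the protocol**

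- Liver criteria, 7.1.2: "Discontinuation of study intervention for abnormal liver tests is required by the Investigator when a participant meets one of the conditions". Leaving the study is not mentioned, and Appendix 5 asks for liver tests to be monitored after IMP is stopped.
- Allergic reaction, 8.2.7: "and study medication must be permanently discontinued". Again only IMP is named.
- Pregnancy, 8.3.5 and 8.3.6: IMP is discontinued and follow-up to the outcome is mandatory.
- Study withdrawal has its own section, 7.2. The list sits in 7.1, which is about stopping the intervention.

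Taken together, this suggests that the safety entries were meant as reasons to stop IMP, but 7.1.1 does not say so.

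**2. Who could be affected**

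Some participants drop out of the question because further follow-up would not change the primary result:

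- Those with NP surgery or any systemic corticosteroid before Week 24 are nonresponders anyway (Protocol 9.3.2).
- Users of intranasal corticosteroid before Week 24 are outside the per-protocol (PP) population (Protocol Table 5).
- Data cannot be required after a participant's own withdrawal.

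What remains is a listed safety event before day 141 in a participant given none of these. SAP Table 10 sets the Week 24 endoscopy window at days 141 to 224, so an endoscopy on or after day 141 would still count.

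**3. The plan's own figure**

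With a true response rate of 62.0% and n = 20, the exact binomial probability of at least 10 responders is 0.908, which agrees with the stated 90%. Also 20/0.8 = 25. The wording problem leaves the sample size statement as it is.

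**4. Primary endpoint, one affected participant**

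A missing Week 24 score counts as nonresponse. SAP Table 3 does not list treatment discontinuation as an intercurrent event for this endpoint, so an observed off-treatment score would have counted. If that participant would have been a responder, the proportion falls by 1/25 = 4.0 points (1/20 = 5.0 points). If not, nothing changes.

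Let q be the probability of response off treatment at Week 24. The documents do not give q, so a range is shown. The others respond at 62%.

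- n = 25, at least 13 responders needed. With a forced nonresponder, P(X ≥ 13 of 24) = 0.842. With the score observed, 0.842 + q × P(X = 12 of 24) = 0.842 + 0.0791q.
- n = 20, at least 10 needed. With a forced nonresponder, P(X ≥ 10 of 19) = 0.859. With the score observed, 0.859 + 0.0785q.

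The loss in the chance of reaching 50%, in percentage points, is about 7.9q at either size:

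| q | Loss (points) |
|---|---|
| 0.1 | 0.8 |
| 0.3 | 2.4 |
| 0.62 (no waning at all) | 4.9 |

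**5. NPS change, one affected participant**

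The stop is not for lack of efficacy, so the missing value is multiply imputed under missing at random. The imputation pool excludes rescued participants and lack-of-efficacy stops (SAP 4.4.1.2), so it is mostly on-treatment data. The regression adjusts for values at all earlier visits, including the participant's own. If the imputed value is d points more favourable than the true off-treatment value, the mean shifts by d/25 = 0.04d (d/20 = 0.05d). The documents give no value for d.

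**6. The two effects together**

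A large loss in step 4 needs q near 0.62, that is, a benefit that persists off treatment. A large d in step 5 needs a benefit that wanes. With waning, q is low and the primary loss is near the bottom of the table. Without it, d is small.

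**The case against.** The strongest reply is that 7.1.1 runs on two tracks: the list covers withdrawal from the study, and the subheading after it covers participants who only stop IMP. Section 7.2 does treat study withdrawal separately. The rule in 7.1 is to remain as long as possible, and the list could define when that is not possible. Sections 7.1.2, 8.2.7 and 8.3.5 are silent on leaving the study, and silence is not contradiction. Section 9.3.3 only encourages visits and expects some gaps. This reading is possible, but 7.1.1 does not state it, and it fits poorly with the follow-up that the protocol requires after a liver signal or a pregnancy. The ambiguity stands.

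Two further points stand in full. Permanent discontinuation is described as rare. And the imputation uses the participant's own scores: any endoscopy before day 141 falls in the Week 4, 8 or 16 window and can enter the model, which limits d.

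A reader might infer that the list threatens the study's conclusion, or add the losses in steps 4 and 5 together. The documents support neither. No number affected is given, no hypothesis test is planned, 50% is a descriptive target, and the two losses rest on opposite assumptions.

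**Conclusion.** The conflict is real: for five safety events, 7.1.1 orders withdrawal from all study procedures, while 7.1, the opening and handling text of 7.1.1 and the treatment-policy handling assume continued follow-up. The consequence is minor. Per affected participant, the primary proportion falls by at most 4.0 points with 25 in PP (5.0 with 20), and in the conservative direction. The mean NPS change may be too favourable by 0.04 points (0.05 with 20) for each point of gap between the imputed and true values. This rests on the event occurring before day 141, on the site following the list literally, and, for NPS change, on an assumed waning of effect. The number affected is probably very small.

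A reader might also infer that all ten reasons should become IMP stops only. The argument here covers the five safety events and gives no ground for removing the other reasons for study withdrawal.

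**What to change.** - In 7.1.1, move the five safety events under permanent discontinuation of IMP. State that these participants continue the scheduled assessments, including the Week 24 endoscopy and the diary, where consent and clinical condition allow.
- Keep own request, Investigator-judged detriment, Sponsor request and critical deviation as reasons for study withdrawal. NP surgery can follow 6.8.1.
- State the CT exception (no CT at an early exit visit, none in pregnancy) in both paragraphs of 7.1.1 and also in 6.8.1 and 7.2. The last two lead to EOT/EOS procedures without it. Otherwise, narrow the Week 24 CT window in SAP Table 10. It runs from just after the first dose to day 265, so a CT at an early exit would count as Week 24.

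The cost is a wording amendment, plus visits that are already scheduled for a few participants who are off treatment. For someone with a malignancy, a serious infection or a pregnancy, a daily diary and endoscopy under local anesthetic and decongestant are a real burden, hence the condition on consent and clinical state.

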7.1.2 Liver chemistry stopping criteria

Details of the liver chemistry stopping criteria are provided in Appendix 5 ([Section 10.5](#)).

Discontinuation of study intervention for abnormal liver tests is required by the Investigator when a participant meets one of the conditions outlined in the algorithm (ie, ALT >3 × ULN) or in the presence of abnormal liver chemistries not meeting protocol-specified stopping rules if the Investigator believes that it is in best interest of the participant.

7.1.3 Temporary discontinuation

Temporary intervention discontinuation may be considered by the Investigator because of suspected AEs or disruption of the clinical study due to a regional or national emergency declared by a governmental agency (Appendix 7: Contingency measures for a regional or national emergency that is declared by a governmental agency [[Section 10.7](#)]). For all temporary intervention discontinuations, the duration should be recorded by the Investigator on the appropriate pages of the e-CRF.

In addition, any of the following conditions will be a cause for temporary treatment discontinuation:

- Infections or infestations that do not respond to medical treatment should have IMP discontinued until the infection is resolved
- Any laboratory abnormality that meets the temporary treatment discontinuation criteria as per Appendix 5 ([Section 10.5](#))

For a participant who requires HBV DNA monitoring, if the HBV DNA result becomes positive during the study, the participant will temporarily discontinue IMP and should be referred to a hepatologist. Investigational medicinal product may be restarted under careful consideration of the participant's risks and benefits based on hepatologist evaluation and current treatment guidelines and after consultation with Medical Monitor (refer to footnote [j](#) in the SoA [[Section 1.3](#)]).

Temporary intervention discontinuation decided by the Investigator corresponds to more than 1 dose not being administered to the participant. If the IMP is interrupted for more than 2 doses, then the participant should permanently discontinue the study intervention.

7.1.4 Rechallenge

Reinitiation of intervention with the IMP will be done under close and appropriate clinical and/or laboratory monitoring once the Investigator has considered, according to his/her best medical judgment, that the IMP was unlikely to have been responsible for the AE in question and that the selection criteria for the study are still met (refer to [Section 5](#)).

For a regional or national emergency declared by a governmental agency, contingency measures are included in Appendix 7: Contingency measures for a regional or national emergency that is declared by a governmental agency ([Section 10.7](#)).

7.2 PARTICIPANT DISCONTINUATION/WITHDRAWAL FROM THE STUDY

- A participant may withdraw from the study at any time at his/her own request or may be withdrawn at any time at the discretion of the Investigator for safety, behavioral, or compliance reasons. This is expected to be uncommon.
- At the time of discontinuing from the study, if possible, an early discontinuation visit should be conducted. See the SoA ([Section 1.3](#)) for data to be collected at the time of EOT/EOS and for any further evaluations that need to be completed.
- If the participant withdraws consent for disclosure of future information, the Sponsor may retain and continue to use any data collected before such a withdrawal of consent.
- If a participant withdraws from the study, he/she may request destruction of any samples taken and not tested, and the Investigator must document this in the site study records.

If participants no longer wish to take the IMP, they will be encouraged to remain in the study.

The Investigators should discuss with them key visits to attend. The value of all their study data collected during their continued involvement will be emphasized as important to the public health value of the study.

Participants who withdraw from the study intervention should be explicitly asked about the contribution of possible AEs to their decision, and any AE information elicited must be documented.

All study withdrawals should be recorded by the Investigator in the appropriate screens of the e-CRF and in the participant's medical records. In the medical record, at least the date of the withdrawal and the reason should be documented.

In addition, a participant may withdraw his/her consent to stop participating in the study. Withdrawal of consent for intervention should be distinguished from withdrawal of consent for

follow-up visits and from withdrawal of consent for non-participant contact follow-up, eg, medical record checks. The site should document any case of withdrawal of consent.

Participants who have withdrawn from the study cannot be retreated in the study. Their inclusion and intervention numbers must not be reused.

7.3 LOST TO FOLLOW-UP

A participant will be considered lost to follow-up if he/she repeatedly fails to return for scheduled visits and is unable to be contacted by the study site.

The following actions must be taken if a participant fails to return to the study site for a required study visit:

- The site must attempt to contact the participant, reschedule the missed visit as soon as possible, counsel the participant on the importance of maintaining the assigned visit schedule, and ascertain whether or not the participant wishes to and/or should continue in the study.
- Before a participant is deemed lost to follow-up, the Investigator or designee must make every effort to regain contact with the participant (where possible, 3 documented attempts via 2 different methods [phone, text, e-mail, certified letter, etc] should be done). These contact attempts should be documented in the participant's medical record.
- Should the participant continue to be unreachable, he/she will be considered to have withdrawn from the study.
- Site personnel or an independent third party will attempt to collect the vital status of the participant within legal and ethical boundaries for all participants enrolled, including those who did not get study intervention. Public sources may be searched for vital status information. If vital status is determined as deceased, this will be documented, and the participant will not be considered lost to follow-up. Sponsor personnel will not be involved in any attempts to collect vital status information.

Discontinuation of specific sites or of the study as a whole are handled as part of Appendix 1 ([Section 10.1](#)).

8 STUDY ASSESSMENTS AND PROCEDURES

- Study procedures and their timing are summarized in the SoA ([Section 1.3](#)). Protocol waivers or exemptions are not allowed.
- Adherence to the study design requirements, including those specified in the SoA, is essential and required for study conduct.
- All screening evaluations must be completed and reviewed to confirm that potential participants meet all eligibility criteria. The Investigator will maintain a screening log to record details of all participants screened and to confirm eligibility or record reasons for screening failure, as applicable.
- Procedures conducted as part of the participant's routine clinical management (eg, blood count, urine tests) and obtained before signing of the ICF may be utilized for screening or baseline purposes, provided the procedures met the protocol-specified criteria and were performed within the time frame defined in the SoA.
- Repeat or unscheduled samples may be taken for safety reasons or for technical issues with the samples.

For a regional or national emergency declared by a governmental agency, contingency measures are included in Appendix 7: Contingency measures for a regional or national emergency that is declared by a governmental agency ([Section 10.7](#)).

